#### 12. SAFETY AND REPORTING PROCEDURES

#### **12.1** Adverse Event

An adverse event (AE) is any untoward medical occurrence in a clinical investigation subject administered a pharmaceutical product during the course of a study and which does not necessarily have to have a causal relationship with this treatment. An adverse event can therefore be any unfavorable and unintended sign (including an abnormal laboratory finding), symptom, or disease temporally associated with the use of an investigational product, whether or not considered related to the medicinal product.

Disease signs, symptoms, and/or laboratory abnormalities already existing prior to the use of the product are not considered AEs after administration of the study product unless they reoccur after the subject has recovered from the pre-existing condition or they represent an exacerbation in intensity or frequency.

A laboratory test abnormality considered clinically relevant (e.g. causing the subject to withdraw from the study, requiring treatment or causing apparent clinical manifestations) or judged relevant by the Investigator should be reported as an adverse event.

An abnormal laboratory value is considered to be an AE if the abnormality:

- results in discontinuation from the study;
- requires treatment, modification/interruption of investigational product dose, or any other therapeutic intervention;
- or is judged to be of significant clinical importance.

Regardless of severity grade, only laboratory abnormalities that fulfill a seriousness criterion need to be documented as a serious adverse event. If a laboratory abnormality is one component of a diagnosis or syndrome, then only the diagnosis or syndrome should be recorded on the AE page/screen of the CRF. If the abnormality was not a part of a diagnosis or syndrome, then the laboratory abnormality should be recorded as the AE. If possible, the laboratory abnormality should be recorded as a medical term and not simply as an abnormal laboratory result (e.g., record thrombocytopenia rather than decreased platelets).

#### 12.2 Adverse Event Documentation

Adverse events will use the descriptions and grading scales found in the revised NCI Common Terminology Criteria for Adverse Events (CTCAE). This study will utilize the CTCAE Version 4.03 for adverse event reporting.

All AEs must be recorded on the electronic case report forms (eCRFs). Documentation must be supported by an entry in the patient's file. Each event should be described in detail along with start and stop dates, severity, relationship to investigational product as judged by the Investigator, action taken and outcome.

#### **12.3** Serious Events

#### A Serious Adverse Event or Reaction is any AE occurring at any dose that:

- results in death;
- is life-threatening;
- requires inpatient hospitalization or prolongation of existing hospitalization;
- results in persistent or significant disability/incapacity;
- in a congenital anomaly / birth defect;
- is an important medical event that may not be immediately life threatening or result in death or hospitalization, but may jeopardize the subject and may require medical or surgical intervention to prevent one of the outcomes listed above (example: intensive treatment in an emergency room or at home for bronchospasm, convulsions that do not result in hospitalization). Medical and scientific judgment should be exercised in deciding whether some events should be considered as serious because their quick reporting to the Sponsor may be of interest for the overall conduct of the study;
- elevated ALT or AST in combination with either an elevated bilirubin or clinical jaundice (suspicious for Drug-Induced Liver Injury [DILI] defined by an elevated ALT or AST (> 3 x baseline value), in combination with either an elevated total bilirubin (> 2 x ULN) or clinical jaundice in the absence of cholestasis or other causes of hyperbilirubinemia);
- Suspected transmission of an infectious agent by the study drug.

**Life-threatening:** The term "life-threatening" in the definition of "serious" refers to an adverse event in which the subject was at risk of death at the time of the event. It does not refer to an adverse event that hypothetically might have caused death if it were more severe.

**Hospitalization:** Any adverse event leading to hospitalization or prolongation of hospitalization will be considered as Serious, UNLESS at least one of the following exceptions is met:

• The admission is pre-planned (i.e., elective or scheduled surgery arranged prior to the start of the study or for prophylactic insertion of a gastric feeding tube).

OR

• The admission is not associated with an adverse event (e.g., social hospitalization for purposes of respite care).

OR

• The admission results in a hospital stay of less than 12 hours

However, it should be noted that invasive treatment during any hospitalization may fulfill the criteria of 'medically important' and as such may be reportable as a serious adverse event dependent on clinical judgment. In addition, where local regulatory authorities specifically require a more stringent definition, the local regulation takes precedent.

**Disability** means a substantial disruption of a person's ability to conduct normal life's functions.

**Important Medical Event:** Any adverse event may be considered serious because it may jeopardize the subject and may require intervention to prevent another serious condition.

**Any Death** (regardless of cause) that occurs from the time of administration of the first dose of protocol therapy until 30 days after the final administration of the study drug, and any death occurring after this time that is judged at least possibly related to prior treatment with the study drug, will be promptly reported.

**Overdose** is defined as the accidental or intentional administration of any dose of a product that is considered both excessive and medically important. All occurrences of overdose must be reported as an SAE.

**SickKids** 

All SAEs must be recorded on eCRFs. All SAEs, whether **related or not related** to study drug, that are thought to be associated with protocol-specified procedures must be collected and reported using SAE Form to Ozmosis within 24 hours of becoming aware of the event.

Pregnancies occurring in study subjects/sexual partner(s) will be treated as per standard procedure for SAEs. Pregnancies occurring in study subjects or their sexual partner(s) after study drug treatment should be reported separately on Pregnancy Report Form and the subject must discontinue the protocol treatment.

# **12.4** Reporting Serious Adverse Events

All serious adverse events must be reported by using the SAE form and must be submitted to *Ozmosis Research Inc*.

#### **Serious Adverse Event Reporting Instructions**

All serious adverse events must be reported as follows:

Within 24 hours: Report initial information by fax or email to:

Ozmosis Research Inc. [contact] [contact]

Email: [contact]

#### The initial information should always contain:

- Name of Reporter/Investigator
- Subject Identification
- Adverse Event Term
- Study Drug Dose and Start/Stop Dates

On the next working day: Fax completed trial-specific Serious Adverse Event form.

## 12.5 Procedures for Expedited Reporting

# 12.5.1 Responsibility for Reporting Serious Adverse Events to Regulatory Authorities

SAEs will be submitted to Regulatory Authorities according to the applicable guidelines and regulations within that country. The Hospital for Sick Children will provide expedited reports of SAEs to Health Canada (including the 7-day notification for death and life-threatening events), i.e. events which are BOTH serious AND unexpected, AND which are thought to be possibly related to protocol treatment (or for which a causal relationship with protocol treatment cannot be ruled out).

The CRO responsible for monitoring sites outside of Canada will be responsible to submitting SAEs to that local Regulatory Authority as per local guidelines and regulations.

# 12.5.2 Responsibility for Reporting Serious Adverse Events to Drug Provider

Ozmosis Research Inc. will be responsible for submitting SAE reports (Initial and/or Follow-up reports) to BMS. The SAE must be reported to BMS by Ozmosis Research Inc. within 24 hours of receipt of the SAE report from the sites. The foregoing is applicable to all SAEs, irrespective of causality.

# 12.5.3 Reporting Serious Adverse Events to Local Research Ethics Boards

Ozmosis Research Inc. will notify all Investigators of all SAEs that are reportable to Regulatory Authorities from this trial or from other clinical trials as reported to BMS. This includes all serious events that are unexpected and related to protocol treatment. Investigators must notify their ethics board/committee according to institutional requirements and file the report with their Investigator Site File. Documentation that SAEs have been reported to ethics board/committee must be kept on file at the CRO as applicable.

#### **Documentation can be any of the following:**

- a letter from the REB acknowledging receipt;
- a stamp from the REB, signed and dated by REB chair, acknowledging receipt;

• a letter demonstrating the SAE was sent to the board.

All expedited serious adverse events occurring within a centre should also be reported to local ethics board/committees.

#### 12.6 Follow up on Adverse and Serious Adverse Events

For the SAEs that have been deemed by the investigator as unrelated to protocol treatment, the SAE reporting period begins on the first date of treatment and ends on the date of Safety Visit or 100 days after discontinuation of the study drug, whichever is later. For the SAEs that have been deemed by the investigator as at least possibly related to protocol treatment, the SAE must be reported even if this occurs after the date of scheduled Safety Visit or past 30 days after discontinuation of the study drug.

The investigator shall provide follow-up information in a new follow-up SAE form. All SAEs must be followed until resolved, become chronic, or stable unless the patient is lost to follow up. Resolution status of such an event should be documented on the eCRF.

The eCRF should capture all AEs occurring from cycle 1 day 1 till the date of Safety Visit or 100 days after discontinuation of the study drug, whichever is later.

In addition, any known untoward event of any severity that occurs subsequent to the AE reporting period that the Investigator assesses as at least possibly related to the protocol therapy (i.e., the relationship cannot be ruled out) should also be reported as an AE.

## 12.7 Relationships

For all AEs, relationship to study drug will be reported on the appropriate AE eCRF page. The Investigator must judge whether the study drug caused or contributed to the AE in which case it is considered to be an adverse drug reaction (ADR), and report it as either:

- 1. Related (definitely, probably or possibly)
  - There is a reasonable possibility that the study drug caused or contributed to the AE.

- This conclusion may be supported by the following observations, though these are not required for the determination of relatedness.
- There is a plausible time sequence between onset of the AE and study drug administration.
- There is a plausible biological mechanism through which study drug may have caused or contributed to the AE.

## 2. Not related (unlikely, unrelated)

- It is highly unlikely or impossible that the study drug caused or contributed to the AE.
  - This conclusion may be supported by the following observations, though these are not required for a determination of not related:
- Another cause of the AE is evident and most plausible.
- The temporal sequence is inconsistent between the onset of the AE and study drug administration; a causal relationship is considered biologically implausible.

# 13. PROCEDURES FOR DISCONTINUATION OF A PATIENT FROM INVESTIGATIONAL PRODUCT

## 13.1 Procedures for Withdrawal from Study

Patient / Legally Acceptable Representative (LAR; such as a parent or guardian, as applicable) are at any time free to withdraw from study (study medication and assessments), without prejudice to further treatment (withdrawal of consent). Such patients and/or their legal guardians will always be asked about the reason(s) and the presence of any adverse events. If possible, they will be seen and assessed by an investigator. Adverse events will be followed up.

Withdrawn patients who meet the criteria to be evaluable for objective response or non-target response as per *Section 10.2.1.2* will not be replaced. Patients who withdraw from the study prior to meeting the criteria to be evaluable in *Section 10.2.1.2* will be replaced on study.

If a patient does not return for a scheduled visit, every effort should be made to contact the patient and/or their legal guardians. In any circumstance, every effort should be made to document patient outcome and reason for withdrawal, if possible. The investigator should request the patient return for a final visit, if applicable and follow-up with the patient regarding any unresolved adverse events.

If the patient and/or their legal guardians withdraw from the trial and also withdraw consent for disclosure of future information, no further evaluations should be performed, and no additional data should be collected. The Study Chair or Co-Chair may retain and continue to use any data collected before such withdrawal of consent.

#### 13.2 Premature Withdrawal/Discontinuation Criteria

- 1. Clinical (including physical examination or serum tumour markers) or radiographic evidence of progressive disease > 12 weeks after start of protocol therapy.
- 2. Adverse Events requiring removal from protocol therapy (See throughout Section 7).
- 3. Patient and/or legal guardian's choice to withdraw from treatment (follow-up permitted by patient and/or legal guardians).
- 4. Patient and/or legal guardian choice to withdraw consent to study (cessation of follow-up).

- 5. Non-compliance that in the opinion of the investigator does not allow for ongoing participation.
- 6. Need for anti-cancer therapy not specified in the protocol.
- 7. Patient lost to follow-up.
- 8. Physician determines it is not in the patient's best interest.
- 9. Repeated eligibility laboratory studies (CBC with differential, bilirubin, ALT (SGPT) or serum creatinine) are outside the parameters required for eligibility prior to the start of protocol therapy (See *Section 8.2*).
- 10. Study is terminated by Sponsor.
- 11. Pregnancy.

Patients who are removed from protocol therapy should continue to have the required observations until the originally planned end of the cycle or until all adverse events have resolved whichever happens later. The only exception is with documentation of the patient's withdrawal of consent. The reason for study removal and the date the patient was removed must be documented in the electronic Case Report Form.

#### 13.3 Off Study Criteria

- 1. 30 days after the last dose of the investigational drug.
- 2. Death.
- 3. Lost to follow-up.
- 4. Withdrawal of consent for any further required observations or data submission.
- 5. Enrollment onto another therapeutic (anti-cancer) study.

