# PROTOCOL SYNOPSIS

Protocol Title:	Pilot Study of Nivolumab in Pediatric Patients with Hypermutant				
Trotocor Title.	Cancers				
Protocol	SickKids Protocol No.: 1000053649				
Number:	Ozmosis Protocol No.: OZM-075				
Sponsor:	[name], The Hospital for Sick Children				
Phase of Development:	Pilot Study				
Methodology:	Single arm pilot study (proof of concept study)				
	Maximum duration of treatment: 24 months. Follow-up: 12 months.				
Study Duration:	Duration of enrollment: 24 months. Estimated duration of the whole				
	protocol: 60 months.				
	Primary Objective:				
	1. To evaluate the objective response rate (ORR) to nivolumab in				
	paediatric patients with refractory or recurrent hypermutated				
	malignancies, including patients with replication repair deficiencies				
	(RRD), such as constitutional mismatch repair deficiency				
	(CMMRD).				
Objectives:	Secondary Objectives:				
	1. To determine the progression free survival (PFS) and overall				
	survival (OS) of paediatric patients with progressive or recurrent				
	hypermutated malignancies, including RRD patients such as				
	CMMRD, treated with nivolumab.				
	2. To evaluate safety and tolerability of nivolumab administered as a				
	single agent at the adult recommended dose of 3 mg/kg every 2				
	weeks. To define and describe the toxicities in paediatric patients				

	with progressive or recurrent hypermutated malignancies including					
	RRD patients, such as CMMRD.					
	Companion Biomarker Exploratory Objectives:					
	1) To explore associations between tumour mutation burden (TMB)					
	and response to nivolumab.					
	2) To discover biomarkers predicting response of hypermutant					
	cancers undergoing PD-1 blockade by investigating tumour					
	neoantigen formation, specific T-cell receptor rearrangements					
	(TCRR) of tumour infiltrating lymphocytes (TILs) and detailed					
	characterization and activation of the immune infiltrations					
	including the TILs.					
	3) To explore the use of minimally invasive methods to monitor and					
	predict response to immune checkpoint inhibition in hypermutant					
	cancers by investigating TCRR, immuno-phenotypic profiling of					
	specific immune cells and their activation as a prognostic factor					
	and variances throughout treatment as a response to therapy. In					
	addition, investigating circulating tumour DNA (ctDNA) from					
	serial peripheral blood samples as a surrogate marker of response.					

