## 3.2 Part II - Treatment and Companion Biomarker Study Duration

Nivolumab will be given in four (4) week cycles (one cycle equals two (2) drug administrations, two (2) weeks apart) for a maximum of up to two (2) years if clinical and radiological benefit is evident. After completion of treatment, patients will enter standard follow up for twelve (12) months. Patients with confirmed disease progression or excessive toxicity will discontinue treatment.

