## 6.2 Dose Modifications for Non-Haematological Toxicity

Patients who have any Grade 3 or Grade 4 non-hematological toxicity attributable to the investigational drug with the specific exclusion of the following, will be removed from the study:

- Grade 3 ALT that returns to levels that meet initial eligibility criteria or baseline within seven (7) days and does not require systemic immunosuppression;
- Grade 3 liver enzyme elevation, including AST/GGT that returns to baseline within 7 days and does not require systemic immunosuppression;
- Grade 3 or 4 serum electrolyte or mineral abnormalities responsive to supplementation;
- Grade 3 or 4 amylase or lipase abnormalities that are not associated with diabetes mellitus (DM), associated liver or gall bladder inflammation or clinical manifestations of pancreatitis;
- isolated Grade 4 amylase or lipase abnormalities that are not associated with symptoms or clinical manifestations of pancreatitis and decrease to < Grade 4 within 1 week of onset;
- Grade 3 rash/oral lesions that resolves to Grade  $\leq 1$  within seven (7) days;
- Grade 3 or 4 seizures (multiple seizures despite medical intervention or life-threatening seizures/status epilepticus) that may occur in the context of pseudo-progression;
- fever greater than 40°C of ≤24 hr. duration;
- Grade 3 fatigue that resolves to Grade  $\leq 2$  within 7 days;
- Grade 3 creatinine increase that resolves to Grade  $\leq 1$  or baseline within seven (7) days.

Patients who experience the following non-hematological toxicities attributable to protocol therapy will also be removed from the study:

- Grade 2 fever that does not resolve to Grade  $\leq 1$  within seven (7) days;
- Grade 2 uveitis, eye pain or blurred vision that does not respond to topical therapy and does not improve to Grade 1 prior to next scheduled dose;
- Grade 2 non-hematological toxicity requiring systemic immunosuppressive therapy. This includes, but is not limited to, autoimmunity of the lung, heart, kidney, bowel, CNS, pituitary or eye;
- Grade 2 endocrine toxicity requiring hormone replacement, with the exception of Grade
   2 hypothyroidism, thyroiditis and thyroid dysfunction adequately managed with thyroid hormone replacement;
- Grade 2 adrenal insufficiency;
- Grade 3 colitis or Grade 3 diarrhea attributable to protocol therapy of more the seven (7) days of duration.

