#### **8.4.1** Tumour Tissue

<sup>17These assessments for C1D1 pre-dose do not need to be repeated if these were done for baseline within seven (7) days prior to C1D1.

<sup>18 Assessments are to be done on days CXD1 ±2 days or CXD15 ±2 days on the day of and prior to nivolumab administration.

<sup>19 Samples may be taken up to 7 days prior to C1D1 dosing.

<sup>20 30 days after last dose.

<sup>21 Every 3 months for 1 year.

<sup>22 Unlike the *Companion Biomarkers*, if the CXD1 of cycle drug administration is delayed or omitted, all *Clinical Assessments* and *Laboratory/ Imaging Investigations* (and their respective windows) should adjust to the new CXD1, reflecting the patient's status prior to the upcoming drug administration. Please see respective footnotes above for details for changes to the *Companion Biomarker* assays.

In order to be included in **Part I** of the study, patients must have at minimum neoplastic specimen available as specified in the *Lab Manual*. With patient consent, said specimens will be assayed using NGS in a specific CLIA–certified laboratory approved by the Study Chair or Co-Chair to assess TMB for eligibility purposes. If this tissue is not available, but a TMB report from the specific CLIA–certified laboratory approved by the Study Chair or Co-Chair is already available, this information can be used for eligibility purposes. Whenever possible, both a fresh, formalin-fixed, paraffin-embedded tumour tissue sample and a fresh frozen tumour tissue sample are preferred to be used for TMB, other *Companion Biomarkers* studies and future biomedical research outlined above. Fresh frozen tissue is highly recommended for affiliated biomarker study once on trial. Please refer to *Lab Manual* for the detailed instructions for submission of the tissues.

In addition, all patients are also highly encouraged to submit paraffin embedded tumour sample to assess for MMR protein expression loss by IHC in a CLIA-certified environment for genes including, but not limited to MLH1, MSH2, MSH6, and PMS2. These results may also be used for inclusion to **Part II**, Cohort C (see above for details). As part of the *Companion Biomarker* studies in **Part II**, immune-related markers including but not limited to CD3, CD4, CD8, CD68, PD-1, and PD-L1 expression will also be assessed by IHC.

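### Section 13.3 takes patients off study 30 days after the last dose, contradicting the 12-month follow-up, the 100-day adverse event window and the overall survival endpoint

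*Protocol*

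**What the plan says.** Section 13.3 of the Protocol gives five off-study criteria. The first is "30 days after the last dose of the investigational drug"; the others are death, loss to follow-up, withdrawal of consent for further observation, and "Enrollment onto another therapeutic (anti-cancer) study". Each is sufficient alone, and none carries an exception for follow-up visits or survival status.

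Elsewhere the Protocol requires activity after day 30:

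- **Synopsis:** "Maximum duration of treatment: 24 months. Follow-up: 12 months", with a stated whole-protocol duration of 60 months.
- **Section 3.2:** "After completion of treatment, patients will enter standard follow up for twelve (12) months".
- **Section 8.2 calendar:** follow-up visits are scheduled "Every 3 months for 1 year" (footnote 21). Disease assessments and the ctDNA and PBMC samples follow the same 3-monthly pattern (footnotes 12, 15 and 16).
- **Section 3.1.1 and calendar footnote 20:** the Safety Visit falls 30 days after the last dose and comes before the Follow-Up Period.
- **Section 10.4.1:** imaging in follow-up is recorded and can count towards best response until a new therapy starts.
- **Section 12.6:** reporting of unrelated serious events "ends on the date of Safety Visit or 100 days after discontinuation of the study drug, whichever is later"; the case report form captures all adverse events over the same window.
- **Synopsis, secondary efficacy measures:** OS runs from first dose to death from any cause. PFS counts progression or death occurring while the patient is on the study.

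Section 13.2 adds a third stopping point: patients taken off therapy are observed to the planned end of the cycle or until adverse events resolve, whichever is later.

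**The concern.** Every patient still under observation 30 days after the last dose meets the first criterion in Section 13.3. The Safety Visit is due at that same point, and the calendar's follow-up begins after it. One section therefore ends the study where another starts the follow-up period.

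The endpoint most exposed is OS. Treatment ends at confirmed progression or excessive toxicity (Section 3.2) or at the 24-month limit. Censoring survivors a month after the last dose ties the censoring time to events that carry prognostic information, so the usual assumption of independent censoring would probably fail and survival would tend to be overstated. The scheduled adverse event window and the follow-up biomarker series are exposed too. If some sites follow Section 13.3 and others follow the calendar, the length of follow-up will differ by site for no clinical reason, and data not collected may not be recoverable.

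**Working it through.** **1. Which rule did the plan assume?** Inputs from the synopsis: "Duration of enrollment: 24 months", up to 24 months of treatment, 12 months of follow-up, 60 months in total.

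- With 12-month follow-up: 24 + 24 + 12 = 60 months. The stated figure reproduces exactly.
- With Section 13.3 as written: 30 days = 30/30.4375 = 0.99 month, so 24 + 24 + 0.99 = 48.99, about 49 months. The stated figure does not reproduce.

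The 30-day criterion is the outlier.

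**2. Scheduled follow-up visits.** Visits at 3, 6, 9 and 12 months have a window of ±14 days. Counting from the last dose, the earliest possible days are:

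- 3 × 30.4375 − 14 = 77.3
- 6 × 30.4375 − 14 = 168.6
- 9 × 30.4375 − 14 = 259.9
- 12 × 30.4375 − 14 = 351.2

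All four are later than day 30, so none would take place. The share of the follow-up year kept is 30/365.25 = 8%.

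**3. Adverse event window.** The Safety Visit window is ±7 days, so it falls no later than day 30 + 7 = 37. The later of the Safety Visit and 100 days is therefore always 100 days (taking discontinuation as the last dose). Section 13.3 keeps 30 of those 100 days; 100 − 30 = 70 days of scheduled capture are lost.

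**4. OS for one patient.** A patient whose last dose is at month 2 would be censored, if alive, at about month 2 + 1 = 3. Under Section 3.2 the same patient would be followed to month 2 + 12 = 14.

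**5. Share of deaths observed (illustration only).** The Protocol gives no survival rate after the last dose. Assume exponential survival from that point with median M months. The probability of death by t months is 1 − 2^(−t/M), taken at t = 0.99 and t = 12.

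| Assumed median M | Dead by day 30 | Dead by 12 months | Share of first-year deaths observed |
|---|---|---|---|
| 3 months | 20.4% | 93.7% | 22% |
| 6 months | 10.8% | 75.0% | 14% |
| 12 months | 5.5% | 50.0% | 11% |

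The last column is the second divided by the third. It describes the case where every site applies Section 13.3 and ignores the calendar.

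**The case against.** The best defence is that one item in a list is set against many operational instructions. The synopsis, Section 3.2 and the calendar all require 12 months of follow-up, and Section 13.2 allows follow-up when a family stops treatment. Most sites would probably follow the calendar. That bears on the likely size of the damage, but nothing in the Protocol says which rule prevails, so the contradiction stands.

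Several stronger readings are tempting, and the document does not support them.

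- **That the follow-up is cancelled.** It remains written in several places. It is contradicted, and the realistic outcome is uneven site practice and incomplete survival data.
- **That most deaths would go unobserved.** This needs a post-treatment survival rate that the Protocol does not give. The table above is conditional on assumed medians.
- **That late immune-related events would be missed.** Section 12.6 keeps at least possibly related events reportable after the window closes, and Section 13.2 continues observation until adverse events resolve. What is at risk is scheduled capture between day 30 and day 100, including of unrelated events.
- **That PFS is broadly biased.** A patient who stops for progression has already had the PFS event. Only those who stop without progression would be censored early.
- **That Section 6.2 is a further exit from follow-up.** It says of patients with certain toxicities "with the specific exclusion of the following, will be removed from the study". Toxicity is not among the Section 13.3 criteria, however, and Section 13.2 and most of the toxicity tables speak of leaving protocol therapy. This is loose wording.
- **That the rule on joining another trial is wrong throughout.** For response it agrees with Section 10.4.1, which stops using imaging once a new therapy begins. Its cost is the loss of survival status.

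It is also fair to say that the primary endpoint is the response rate, and that the Protocol attaches no hypothesis test or power claim to OS or PFS.

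**Conclusion.** The concern holds as an internal contradiction. Section 13.3(1) conflicts with the synopsis, Sections 3.2, 8.2 and 12.6, and the definition of OS, and no other text reconciles them. The Protocol's own 60-month total shows that the 12-month follow-up was intended.

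If Section 13.3 were followed literally, all four scheduled follow-up visits and about 11 of 12 months of follow-up would be lost, with 70 of 100 days of routine adverse event capture. OS would be censored about 1 month after the last dose. That this censoring would be informative is a judgement, resting on the stated reasons for stopping treatment; its size cannot be computed from the document.

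The effect on PFS is limited to patients who stop without progression. The primary response rate is largely unaffected, apart from any response first seen in follow-up imaging before a new therapy.

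**What to change.** Amend the wording of Sections 13.2 and 13.3 to agree with Sections 3.2, 8.2 and 12.6:

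- Define off treatment and off study separately.
- Replace the 30-day criterion in Section 13.3(1) with completion of the 12-month follow-up.
- State that survival status is collected through that period, including after enrolment on another trial (Section 13.3(5)), unless consent to further data collection is withdrawn. Response assessment can still end when a new therapy starts, as Section 10.4.1 provides.
- State how the observation rule at the end of Section 13.2 relates to the 100-day window and the follow-up year.
- Reconcile the study-removal wording in Section 6.2 with the protocol-therapy wording used elsewhere, without altering any rule on stopping treatment.

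The cost is a text amendment and a notice to sites. The visits are already in the study calendar, so no new procedure is added; the one extension is survival status after a patient joins another trial. The Protocol shows no budget, so nothing can be said about funding.
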